### Week 3 (Cross-over: Day 15)

Participants switched interventions:

- Those who previously consumed blueberry water in Week 2 now consumed placebo sweet water.
- Those who previously consumed placebo sweet water in Week 2 now consumed blueberry water.

#### Biological sample collection:

- Urine and blood samples were collected at multiple time points over a 24-hour period.
- Fecal samples were collected at different time points over a 48-hour period.

Participants continued to avoid consuming soymilk, green tea, and blueberry products until Day 17.

## 3. Dietary Flavonoids (Green Tea) Consumption and Placebo

### Week 1 (Wash-in Period: Days 1–7)

Sixteen (16) healthy volunteers were recruited and instructed to avoid consuming soymilk, green tea, and blueberry products starting one week before the intervention and continuing throughout the entire three-week study period.

### Week 2 (First Intervention: Day 8)

Participants were randomized into two groups:

- **Green tea-first group:** Consumed a breakfast including 460 mL of green tea in a single dose.

- **Control-first group:** Consumed a breakfast including 460 mL of water in a single dose.

#### **Biological sample collection:**

- Urine and blood samples were collected at multiple time points over a 24-hour period.
- Fecal samples were collected at different time points over a 48-hour period.

Participants continued to avoid consuming soymilk, green tea, and blueberry products.

#### **Week 3 (Cross-over: Day 15)**

Participants switched interventions:

[figure not shown]
- Those who previously consumed green tea in Week 2 now consumed water.
- Those who previously consumed water in Week 2 now consumed green tea.

#### **Biological sample collection:**

[figure not shown]
- Urine and blood samples were collected at multiple time points over a 24-hour period.
- Fecal samples were collected at different time points over a 48-hour period.

Participants continued to avoid consuming soymilk, green tea, and blueberry products until Day 17.

**Scheme 1. Recruitment, screening, and enrollment for each PK study**

## Scheme 2. Experimental design and sample collections of the acute PK study with a crossover design

| Calendar for Fecal Sample Collection_Human Study_2023   |   |   |  |       |               |               |
|---|---|---|--|-------|---------------|---------------|
| Day 0 (Consenting)  | Day 1   | Day 2   | Day 3  | Day 4 | Day 5         | Day 6         |
| Day 7 
 
○ Pick up cooler and fecal collector;
 
    | Day 8 (Control) 
 
○ Collect baseline (0 h) fecal samples;
 
○ Bring baseline fecal sample to HRC;
 
○ Pick up another cooler and fecal collector;
 
○ Collect 24-h fecal samples;
 
 | Day 9 
 
○ Bring 24-h fecal sample to HRC;
 
○ Pick up another cooler and fecal collector;
 
○ Collect 48-h fecal samples;
 
  | Day 10 
 
○ Bring 48-h fecal sample to HRC;
 
○ Pick up another cooler and fecal collector;
 
 |       | Day 11 | Day 12 |
| Day 14 
 
○ Collect baseline (0 h) fecal samples;
 
 | Day 15 (Treatment) 
 
○ Bring baseline fecal sample to HRC;
 
○ Pick up another cooler and fecal collector;
 
○ Collect 24-h fecal samples;
 
   | Day 16 
 
○ Bring 24-h fecal sample to HRC;
 
○ Pick up another cooler and fecal collector;
 
○ Collect 48-h fecal samples;
 
 | Day 17 
 
○ Bring 48-h fecal sample to HRC;
 
  |       | Day 18 | Day 19 |
|   |   |   |  |       |               | Day 20 |

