#### Week 2 (First Intervention: Day 8)

Participants were randomized into two groups:

- **Soymilk-first group:** Consumed a breakfast including 460 mL of soymilk in a single dose.
- **Control-first group:** Consumed a breakfast including 460 mL of milk in a single dose.

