#### Biological sample collection:

- Urine and blood samples were collected at multiple time points over a 24-hour period.
- Fecal samples were collected at different time points over a 48-hour period.

Participants continued to avoid consuming soymilk, green tea, and blueberry products.

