#### Week 3 (Cross-over: Day 15)

Participants switched interventions:

- Those who previously consumed soymilk in Week 2 now consumed milk.
- Those who previously consumed milk in Week 2 now consumed soymilk.

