## Statistical Analysis Plan

The primary objective of this study is to evaluate whether dietary flavonoids from soy milk, blueberries and green tea can trap reactive carbonyl species in humans by detecting the formation of carbonyl adducts of these flavonoids.

Statistical Analysis: ANOVA with repeated measures and post hoc comparisons will be conducted to identify metabolites that show significant differences across various time points or treatments.

Power Analysis: A sample size of n=16 subjects per group will provide 80% power to detect metabolites with an effect size of 0.809, which is sufficient to assess the expected trapping effects of dietary flavonoids.

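### The stool calendar lists the 0 h sample on the dosing day in period 1 but on the day before dosing in period 2, and the SAP names no period term

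*Combined protocol and SAP*

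**What the plan says.** The Study Design section describes a randomised crossover with 16 healthy adults for each intervention. Under Study Methods- Procedures, each product is compared with its control on two dosing days, Day 8 and Day 15, and the order is randomised ("Participants were randomized into two groups"). On stool, the procedures say only "Fecal samples were collected at different time points over a 48-hour period".

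The detail is in Scheme 2, in the table titled "Calendar for Fecal Sample Collection_Human Study_2023". The relevant cells read as follows.

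- **Day 7:** pick up a cooler and collector; no collection is listed.
- **Day 8 (dosing, period 1):** "Collect baseline (0 h) fecal samples", then "Bring baseline fecal sample to HRC", then start on the 24 h sample.
- **Day 14:** "Collect baseline (0 h) fecal samples".
- **Day 15 (dosing, period 2):** "Bring baseline fecal sample to HRC", then start on the 24 h sample; no baseline collection is listed.

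The Statistical Analysis Plan specifies repeated-measures ANOVA with post hoc comparisons, to find metabolites with "significant differences across various time points or treatments". It names no period, sequence or period-by-time term.

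**The concern.** A crossover relies on the two periods being alike apart from the treatment given. If the 0 h stool is taken at a different point relative to dosing in each period, the two baselines are not quite the same measurement. Any resulting difference in adduct level enters fecal change from 0 h as a period effect located at 0 h only. The model as named has no term to absorb it.

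At stake is the precision of fecal change from 0 h and, if the sequences are unequal in size, a small bias in the product-control contrast for that change. Direct product-control comparisons at 24 h or 48 h do not use the 0 h stool.

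**Working it through.** **The timing.** Collection day minus dosing day for the 0 h stool:

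- Period 1: Day 8 − Day 8 = 0 days.
- Period 2: Day 14 − Day 15 = −1 day.

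These are calendar days. Without clock times, the difference in hours is unknown.

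**The plan's power figure.** The SAP gives 80% power at n = 16 per group and effect size 0.809. It states no alpha, sidedness or type of effect size, so the figure cannot be reproduced from its own inputs. At an assumed two-sided 5%:

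- paired t-test, 16 participants: noncentrality 0.809 × √16 = 3.236 on 15 df, power 85.6%;
- paired t-test, 14 participants: 79.9%;
- two-sample t-test, 16 per group: 60.0%.

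The paired reading is used below as an assumption. The concern does not depend on the 80%.

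**Set-up.** Let π be the shift in the period 2 0 h value caused by the earlier collection, and τ the true product-control difference in change from 0 h. Both are in units of the SD of the paired difference. The documents give neither π nor the sequence sizes, so both are varied. A participant's product-minus-control difference in change is then:

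- product-first (control in period 2): D = τ + π;
- control-first (product in period 2): D = τ − π.

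**Bias without a period term.** With n₁ product-first and n₂ control-first, bias = π(n₁ − n₂)/16. The table gives its size; the sign depends on the direction of the shift and on which sequence is larger.

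| Sequences | π = 0.1 | π = 0.3 | π = 0.5 |
|---|---|---|---|
| 8/8 | 0 | 0 | 0 |
| 7/9 | 0.0125 | 0.0375 | 0.0625 |
| 6/10 | 0.025 | 0.075 | 0.125 |

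A least-squares fit of the time-point model (participant, time at 0, 24 and 48 h, treatment, treatment-by-time) gives these same values for the treatment-by-time contrast at 24 h and at 48 h. Adding a period main effect leaves them unchanged: it moves all three times equally and so cancels in change from 0 h. Adding period-by-time makes them zero.

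**Precision at 8/8.** Without a period term, the ±π split is counted as random variation. The expected variance of D becomes 1 + (16/15)π², which is 1.096 at π = 0.3 and 1.267 at π = 0.5. The estimate itself is no more variable, so the paired t-test becomes conservative. Simulation (400,000 runs per cell, two-sided 5%) gives:

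| π | Power, no period term (df 15) | Power, period term on change (df 14) | Rejection at τ = 0, no period term |
|---|---|---|---|
| 0 | 85.6% | 85.3% | 5.0% |
| 0.1 | 85.4% | 85.3% | 4.8% |
| 0.3 | 83.3% | 85.3% | 4.1% |
| 0.5 | 79.0% | 85.3% | 3.0% |

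**Price of the period term when there is no shift.** The estimate is the mean of the two sequence means, with SE = ½√(1/n₁ + 1/n₂):

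- 8/8: SE 0.250, power 85.3%;
- 7/9: SE 0.252, power 84.7%;
- 6/10: SE 0.258, power 83.0%.

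The comparison is 85.6% without the term.

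**The case against.** The best defence is that the calendar is loose about days. It lists the 24 h collection on the dosing day and the 48 h collection on the day after, each delivered a day later. A collection entry may therefore mark when the collector is in hand, not the nominal hour. Both baselines are delivered on the dosing day, so an evening sample on Day 14 against a morning sample on Day 8 would differ by hours.

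Part of this stands. No clock times are given, and a full one-day gap is not established. But the reading does not align the two baselines: the period 1 collector is picked up on Day 7, and collection is still listed on Day 8.

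The extracted table is also damaged (Day 13 is absent), and figures are missing nearby that might have shown sampling times. Still, the entries for Days 7, 8, 14 and 15 fit together, and this is the only detailed stool schedule in the available text.

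It can fairly be added that the SAP never says stool will be analysed as change from 0 h, that the shift and the unequal splits are assumptions, and that adduct levels may hardly move in a day while participants avoid the three foods. All of that stands and limits the size of the point.

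A reader might infer something stronger from the calendar's labels, which mark Day 8 as control and Day 15 as treatment: that everyone took control first, so the earlier baseline always went with the product. The documents do not support this. The procedures randomise the order and state the switch in both directions (for example, "Those who previously consumed soymilk in Week 2 now consumed milk"). A calendar for the product-first order may simply not be in the available text.

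**Conclusion.** The concern holds as a minor point about fecal change from 0 h. The calendar lists the two baselines on different days relative to dosing, and the named model has no term for period.

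With equal sequences there is no bias and no inflation of false positives. The cost is at most a few points of power: about 2 at an assumed 0.3 SD shift and about 6 at 0.5 SD (79.0% against 85.3%), and possibly almost none. With unequal sequences the bias reaches 0.0625 SD at 7/9 and 0.125 SD at 6/10 for a 0.5 SD shift.

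These figures rest on an assumed shift, assumed splits, two-sided 5% testing, 0.809 read as a standardised paired difference, and a baseline difference that follows period. If it followed treatment instead, period terms would not remove it; the documents do not show that it does.

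A reader might also infer that the fecal results are biased, or that blood and urine are affected or are safe. The first does not follow under equal sequences. The second cannot be judged, because the documents give no sampling times for blood or urine.

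**What to change.** - **Sampling:** set one pre-dose window for the 0 h stool in both periods, for example the last stool in the 24 h before the test drink (24 h is a suggestion), and record the clock time.
- **Model:** include period in the crossover analysis and analyse by the sequence actually followed. For stool, add a period-by-time term, or fit a period term to each participant's per-period change from 0 h. A period main effect alone is not enough in the time-point model.
- **If sampling is complete**, as the past-tense procedures and the 2023 calendar suggest it may be, apply the model terms and report the actual 0 h stool timing by period and by sequence followed.

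The cost is one sentence on the window, one time entry per sample and the extra terms, with no added visits or samples. On change scores the period term uses 1 of 15 degrees of freedom; at 8/8 with no shift that is 0.3 percentage points of power. In a model with 0, 24 and 48 h as levels, period plus period-by-time uses 1 + 2 = 3 degrees of freedom.

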## Statistical Analysis Plan

The primary objective of this study is to evaluate whether dietary flavonoids from soy milk, blueberries and green tea can trap reactive carbonyl species in humans by detecting the formation of carbonyl adducts of these flavonoids.

Statistical Analysis: ANOVA with repeated measures and post hoc comparisons will be conducted to identify metabolites that show significant differences across various time points or treatments.

Power Analysis: A sample size of n=16 subjects per group will provide 80% power to detect metabolites with an effect size of 0.809, which is sufficient to assess the expected trapping effects of dietary flavonoids.

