## Study Objectives

The goal of this study is to determine the formation and kinetics of reactive carbonyl adducts of dietary flavonoids (soymilk, blueberry and green tea) in humans after a single dose of the dietary flavonoids. We speculate that the dietary flavonoids (soymilk, blueberry and green tea) can react with endogenous reactive carbonyls species to form reactive carbonyl adducts in the body, eventually alleviating the damaging effects of reactive carbonyls species on human health. Study on the formation and kinetics of reactive carbonyl adducts of dietary flavonoids is also expected to be able to provide substantial evidence for the health effects of regular dietary flavonoids (soymilk, blueberry and green tea) consumption in epidemiological studies.

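### The planned repeated-measures ANOVA does not name period, although each product is tested in a randomised two-period crossover

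*Combined protocol and SAP*

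**What the plan says.** For each of the three products, the procedures describe the same design. On Day 8, "Participants were randomized into two groups", product first or control first. On Day 15 they switch: "Those who previously consumed milk in Week 2 now consumed soymilk", "Those who previously consumed placebo sweet water in Week 2 now consumed blueberry water" and "Those who previously consumed water in Week 2 now consumed green tea". Each product therefore has a two-sequence, two-period crossover in 16 people.

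Sampling is repeated within each visit: "Urine and blood samples were collected at multiple time points over a 24-hour period", with faecal samples over 48 hours. The Study Objectives section says: "The goal of this study is to determine the formation and kinetics of reactive carbonyl adducts of dietary flavonoids".

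The only analysis text is in the Statistical Analysis Plan: "ANOVA with repeated measures and post hoc comparisons will be conducted to identify metabolites that show significant differences across various time points or treatments". Neither period nor sequence appears there or elsewhere as a model term. The procedures use the phrase time points for sampling within a visit, and nothing extends it to Day 8 versus Day 15.

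The same section states 80% power with 16 per group at an effect size of 0.809. It gives no alpha, sidedness, test or definition of the effect size.

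**The concern.** Order is randomised in a crossover so that a difference between the two days can be separated from the difference between product and control. An analysis with treatment and sampling time only does not use that information. Anything that moves adduct levels between Day 8 and Day 15 is then left in the error when the orders are balanced, and partly in the treatment estimate when they are not.

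With 16 people per product, the practical risk is a missed overall product-versus-control difference. A second risk is an estimate shifted up or down by an accident of allocation or dropout.

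**Working it through.** **The plan's own figure.** With 0.809 read as a standardised difference and two-sided alpha 0.05 (both assumed), a paired t-test in 16 people has 85.6% power, and a two-sample t-test with 16 per arm has 60.0%. Neither gives the stated 80%, and the missing inputs leave the figure undetermined. The point here does not depend on it. The paired reading is used below.

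**Set-up.** Let D be each participant's product-minus-control difference averaged over sampling times, in units of its own SD. Let π be the Day 8 minus Day 15 difference in those units. The mean of D is τ + π for the n1 people with product first and τ − π for the n2 with control first. The documents give neither π nor the split. I take π = 0.3 and 0.5, and splits from 8:8 to 12:4.

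**Period omitted (paired t, 15 df).**
- Mean of the estimate: τ + π(n1 − n2)/16.
- At 8:8 the true standard error is 1/√16 = 0.25, but the expected sample variance is 1 + π² × 16/15. At π = 0.5 this is 1.267, so the reported standard error is about √1.267/4 = 0.281. The test is unbiased but conservative.
- Simulated power at 8:8 for τ = 0.809: 83.3% at π = 0.3 and 79.0% at π = 0.5.

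**Period fitted (14 df).** The standard error is √[(1/n1 + 1/n2)/4], and the noncentrality is 0.809 divided by it: 0.809/0.25 = 3.236 at 8:8, and 0.809/0.2887 = 2.802 at 12:4. Bias is zero and type I error is 5% at every split.

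| Split | Share of π in the estimate, period omitted | Type I error, period omitted, π = 0.3 / 0.5 | Power, period fitted |
|---|---|---|---|
| 8:8 | 0 | 4.1% / 2.9% | 85.3% |
| 10:6 | 4/16 = 25% | 5.0% / 4.9% | 83.0% |
| 11:5 | 6/16 = 37.5% | 6.1% / 7.5% | 79.7% |
| 12:4 | 8/16 = 50% | 7.7% / 11.6% | 74.1% |

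At π = 0.5 with period omitted, power is 64% or 90% at 10:6, and 48% or 96% at 12:4, depending on the direction of the shift.

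**Averaged over the randomisation.** The method of randomisation is not stated. Under simple randomisation (assumed), 8:8 occurs 20% of the time, 9:7 35%, 10:6 24%, 11:5 13%, and 12:4 or more unequal 8%. Averaged over these, the unadjusted test has type I error 5.0% and mean bias zero at π = 0, 0.3 and 0.5. Its power is about 86%, 83% and 77%, against about 83% with period fitted.

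**What is not affected.** A shift that is the same at every sampling time cancels from any contrast made within a visit. In one simulated data set with shifts of 0, 0.5 and 1.0, the treatment-by-time F was 0.3460 each time and the change-from-0 h statistic was 0.3690 each time. The squared paired t on the time averages moved from 0.0374 to 0.0261 to 0.0144.

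**The case against.** The strongest reply is that this is a routine gap with uncertain consequence. The documents give no period difference, and food restrictions and procedures are the same around both days. With no period effect the omission does no harm. Under simple randomisation, fitting period costs about 3 points of power if there is no period effect, breaks even at about 0.3 SD, and gains about 5 to 6 points at 0.5 SD. All of that stands. It limits the size of the point, but does not supply the missing specification.

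It can also be said that the affected contrast is not one the plan singles out. The stated goal includes kinetics, and treatment-by-time tests are immune to a constant shift. So is change from the same period's 0 h value; the faecal calendar in Scheme 2 lists "Collect baseline (0 h) fecal samples" before each intervention. This stands too. However, the analysis sentence looks for differences across treatments as well as across time points, and nothing limits inference to within-visit contrasts.

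A reader might infer three stronger criticisms that the documents do not support:
- **That the plan has an inflated false-positive rate.** Inflation arises only conditional on a split of about 11:5 or worse, and no split is reported.
- **That the ANOVA ignores correlation among samples from one visit.** A participant-only mixed model would do so, but the plan does not propose one. A standard two-way within-subject ANOVA tests treatment against participant-by-treatment error, and held 4.9% to 5.1% in simulation with visit effects present.
- **That a missing sequence term is itself a defect.** With complete data, sequence does not change the within-person estimate.

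**Conclusion.** The concern holds as a specification gap for the overall product-versus-control comparison. With balanced orders the consequence is lost power without bias: 83% or 79% against 85%, for an assumed period difference of 0.3 or 0.5 SD. With unequal orders the estimate carries (n1 − n2)/16 of the period difference. The type I consequence is conditional on the realised split and averages out over simple randomisation. These figures rest on two-sided alpha 0.05, on 0.809 being in SDs of the within-person difference, and on assumed period differences.

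One related inconsistency needs an answer. The faecal calendar in Scheme 2 labels Day 8 as control and Day 15 as treatment, whereas the procedures randomise the order. A reader might infer that everyone had control first. The calendar may only illustrate one sequence, so that inference is not secure. It matters because under a single fixed order period and treatment could not be separated by any model.

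**What to change.** For each product against its own control, add period as a fixed effect to the repeated-measures model alongside treatment, time and treatment-by-time. State that the treatment effect is tested against between-visit error within participants (participant and participant-by-period terms). Equivalently, for the overall effect, use a period-adjusted two-sequence analysis of each participant's product-minus-control difference, with 14 error degrees of freedom. The per-person summary must be the same pre-specified one in both formulations: an AUC weights by sampling interval and does not in general equal the unweighted time average. A sequence term is optional. Report how many participants had each order, and reconcile the Scheme 2 calendar with the randomised order.

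The cost is wording, standard software and one error degree of freedom. If there is no period effect, power goes from 85.6% to 85.3% at 8:8, and to 83.0% at 10:6 or 74.1% at 12:4. The period term does not remove carry-over in participants who had the product first.

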## Study Design

This study follows a **randomized, crossover design**, where participants will consume each intervention (soymilk, blueberry, and green tea) in separate study periods with a washout phase in between.

- **Study Duration:** 17 days
- **Number of Participants:** 16 healthy adults for each intervention
- **Intervention Groups:**
  - Dietary Flavonoids (Soymilk) Consumption and Placebo
  - Dietary Flavonoids (Blueberry) Consumption and Placebo
  - Dietary Flavonoids (Green Tea) Consumption and Placebo

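### The SAP names repeated-measures ANOVA with no rule for missing samples; in its complete-case form, 5% missing stools would leave about 12 of 16 participants in the stool analysis

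*Combined protocol and SAP*

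**What the plan says.** The Statistical Analysis section states that "ANOVA with repeated measures and post hoc comparisons will be conducted", with the aim "to identify metabolites that show significant differences across various time points or treatments". It names no software, covariance structure or estimation method, and does not say what happens to a participant with a missing sample. No allowance for dropout or lost samples is stated.

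The sample size is "16 healthy adults for each intervention" (Study Design), each person crossing over between one food and its control. The Power Analysis says "A sample size of n=16 subjects per group will provide 80% power" for an "effect size of 0.809".

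On sampling, the Procedures say "Urine and blood samples were collected at multiple time points over a 24-hour period" and "Fecal samples were collected at different time points over a 48-hour period", repeated for both periods of each food. The Scheme 2 calendar fixes the stool times: it begins with "Collect baseline (0 h) fecal samples", follows with 24 h and 48 h samples, and repeats all three around Day 15. That is six stools per person. The text gives no number of blood or urine times; figures not reproduced in the copy reviewed may show it.

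**The concern.** A classical repeated-measures ANOVA works on a complete participant-by-time-by-treatment table. If one cell is empty, standard practice drops the participant from that table, and the other samples of that type from both periods go unused. A stool cannot be produced on demand in a fixed window, so some empty cells should be expected.

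With only 16 participants per food there is little slack. If the rule is not written down, the choice between dropping people and using what was collected will be made with the data in view, and across many metabolites it could be made differently each time.

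**Working it through.** **Inputs from the documents.** 16 participants per food; effect size 0.809; stated power 80%; six stools per person (three times, two periods).

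**Assumptions.** Two-sided alpha of 0.05; 0.809 read as a paired standardised difference; samples missing independently at a common rate q; each sample type analysed separately; 16 blood or urine samples per person (8 times in 2 periods), with 12 to 20 as a range.

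**Step 1: the plan's own figure.** The exact noncentral-t power of a paired test with n = 16 and effect 0.809 is 85.6%, not 80%. Read as two independent groups of 16, it is 60.0%. Neither reading reproduces 80%, and the plan states no alpha, test or type of effect size. The paired reading fits the crossover and is used below. Paired power by number of complete participants:

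| Complete | 16 | 15 | 14 | 13 | 12 | 11 |
|---|---|---|---|---|---|---|
| Power | 85.6% | 83.0% | 79.9% | 76.4% | 72.3% | 67.7% |

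**Step 2: complete participants.** With m samples per person, the chance that one person is complete is (1 − q)^m, and the expected number complete is 16 × (1 − q)^m. For example, 0.95^6 = 0.735 and 16 × 0.735 = 11.8. Power is the paired power averaged over a binomial number of complete participants.

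| Sample type | q | (1 − q)^m | Expected complete of 16 | Average power |
|---|---|---|---|---|
| Stool, m = 6 | 1% | 0.941 | 15.1 | 83% |
| Stool, m = 6 | 2% | 0.886 | 14.2 | 80% |
| Stool, m = 6 | 5% | 0.735 | 11.8 | 70% |
| Stool, m = 6 | 10% | 0.531 | 8.5 | 53% |
| Blood or urine, m = 16 (assumed) | 2% | 0.724 | 11.6 | 70% |

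At 2% missing, the range m = 12 to m = 20 gives 12.6 to 10.7 complete and power of 74% to 65%.

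**Step 3: the same loss as a count.** One food yields 16 × 6 = 96 stools. Since k missing samples remove at most k people, three missing leave at least 13 (13.2 on average), five leave 11.5 on average and eight leave 9.4 on average.

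**Step 4: what using all available samples recovers.** Simulated stool data used assumed variances (participant 1, participant-by-period 0.25, residual 0.75) and a post-dose effect of 0.78. The difference between two period means of two post-dose samples has variance 2 × (0.25 + 0.75/2) = 1.25, so the paired effect is 0.78/√1.25 = 0.70, with power of about 74% when complete. The first, second and fourth rows are from 20,000 replicates; the mixed model is from 300, with a standard error of about 2.5 points.

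| Analysis | 5% missing | 10% missing |
|---|---|---|
| Drop anyone without all six stools | 58% | 43% |
| Drop anyone without all four post-dose stools | 64% | 52% |
| Mixed model, all post-dose stools | 73% | 71% |
| Paired test on each person's available post-dose mean | 72% | 69% |

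With no missing data, the 300-replicate run gave 77% for the complete-case test and 76% for the mixed model. Rejection under the null was 4.3% to 6.3% for the mixed model. These runs had no period or sequence terms.

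**The case against.** The strongest reply is that the plan does not say it will drop anyone. The phrase it uses can also describe a repeated-measures model fitted to incomplete data. That stands: deletion is a risk the wording permits, not a documented rule.

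A reader might infer that a handful of lost samples would destroy the trial. The arithmetic does not support that. Losing half the participants needs at least eight missing samples, each from a different person. A missing stool need not affect the blood or urine analysis if the sample types are analysed separately, as seems likely. At 1% to 2% missing stools, power stays at or above the plan's 80%. The documents give no missing rate, so the benign end cannot be excluded.

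A reader might also infer that slow gut transit would make the complete participants a biased subset. The documents offer nothing on this, the calculations assume random missingness, and a mixed model would not repair it if missingness depended on unobserved values.

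Finally, the gain in Step 4 is not peculiar to the mixed model. A paired test on available means does nearly as well, and part of the gap to the six-stool rule comes from people dropped for a missing baseline that the comparison never uses. That also stands: the benefit comes from using the samples collected. The mixed model remains the better replacement because it estimates the time course the plan asks about and adjusts for time when the missing windows differ between periods, which a simple mean does not.

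**Conclusion.** The concern holds as a gap with a potentially large effect. The SAP names a method whose classical form needs complete data, sets no missing-sample rule, and asks for at least six samples per person in one sample type. If the complete-case form were used, power would fall from 86% to about 83% to 80% at 1% to 2% missing stools, to 70% at 5% and to 53% at 10%. Under the paired reading, the stated 80% is effectively used up once two participants are lost (79.9% at 14).

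These figures rest on assumed missing rates, independent missingness, a paired effect of 0.809 and two-sided 0.05; the blood and urine figures also rest on an assumed number of samples. The retention figures need only the missing rate, independence and the sample count.

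**What to change.** Replace the repeated-measures ANOVA in the SAP with a linear mixed model fitted by REML to all available samples, separately for each adduct and sample type within each food's crossover:

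- Fixed effects: treatment, time, treatment-by-time, period and sequence.
- Random effects: participant and participant-by-period.
- Kenward-Roger or Satterthwaite degrees of freedom.
- No participant excluded for a missing time point.
- The missing-at-random assumption stated.
- Numbers of samples and participants analysed reported by sample type and period.
- A complete-case analysis as a sensitivity analysis.

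The cost is SAP wording and slightly more analysis work, with no new samples. With complete data, power is essentially unchanged. The model does not remove bias if samples are missing for reasons tied to unobserved values, so the missing counts should be read with that limit in mind.
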